7.2.4 Adverse Events

The Investigator and designated study personnel will monitor each participant for AEs during the study. All AEs reported between consent and final follow-up will be recorded in the CRF. All AEs reported before administration of study product will be entered in to the Medical History sections of the CRF, and all other AEs reported in the AE section of the CRF. All SAEs will be captured in the AE section of the CRF from time of consent. All AEs deemed to be signs of genital irritation (as identified in Section 8.3) will be designated as such in the CRF. In addition, abnormal vaginal discharge considered to be leakage of the gel will be designated as such in the CRF and will not be considered to be an AE. The investigator or designee will ask the participant's non-leading questions in an effort to detect AEs. Examples of these are:

```
"How are you feeling?"
```

or

In addition, participants should be encouraged to spontaneously report any unusual feelings or sensations at the study visits and between visits on the study diary card. See Section 8 for full details on adverse experience reporting.

7.2.5 Normal Vaginal Discharge

A normal physiological vaginal discharge is a mix of secretions from the cervical mucus glands and desquamation of vaginal epithelial cells. It is often described as being colorless and white or milky in appearance, drying to a yellow on underwear.

The color, consistency, and associated odor for an individual woman may vary at different stages of the menstrual cycle and can also be affected by method of contraception, and other factors. It is acidic, with a normal pH of 4.5 and associated with a predominant flora of lactobacilli.

Because of the wide individual and population variability in the appearances of normal vaginal discharge, in clinical practice it is often the patient perception of a change from her expected pattern in amount, consistency, associated odor, or development of other symptoms that will determine whether vaginal discharge is normal or abnormal.

[&]quot;Since you were last asked, have you felt unwell or different from usual?"

7.2.6 Laboratory Testing

7.2.6.1 STI Screen

Tests for the following STIs will be conducted at the Screening visit and if clinically indicated during the study:

- Chlamydia according to local practice
- Gonorrhea according to local practice
- Trichomoniasis by wet mount vaginal smear or according to local practice

Any participant found to be positive for an STI requiring treatment will not be permitted to enter the study until the infection has completely resolved (confirmed by re-testing) and treatment has been completed for at least 14 days prior to enrolment. Participants diagnosed during the study will be required to withdraw from the study and all details of the diagnosis and treatment must be recorded in the CRF.

Full details on all assays are outlined in the Study Procedures Manual.

7.2.6.2 Urinalysis

Conducted at Screening and each visit:

• Urine dipstick (with microscopy if required) to determine abnormalities suggestive of bacterial UTI

Note: The presence of leucocytes, proteinuria, hematuria and a positive nitrite test is indicative of UTI. The presence of trace proteinuria alone should not be sufficient for a presumptive diagnosis of UTI.

7.2.6.3 Assessment of BV

During the pelvic exam at each visit, a wet mount vaginal smear will be performed and the pH of the lateral vaginal wall determined to assess the presence of BV. A dry mount vaginal smear will also be performed for Gram stain and Nugent Symptom Scoring.

A diagnosis of BV will be determined according to the following criteria:

- At screening all of the following symptoms from the Amsel's Criteria¹⁵ will need to be present to indicate a diagnosis of BV: presence of white to grey homogenous discharge; positive whiff test (amine odor with addition of potassium hydroxide (KOH)); pH greater than 4.5; presence of clue cells with a decrease in lactobacilli morphotypes, and increase in non-lactobacilli morphotypes. Thereafter a diagnosis of BV will be indicated by the presence of three out of the four criteria above.
- In addition, the Gram stained smear will be scored according to the Nugent's method¹⁶ to determine the status of the vaginal flora. A score of 0-3 indicates normal vaginal flora, a score of 4-6 indicates intermediate flora, and a score of 7-10 indicates a microbiological

diagnosis of BV. At screening, a score of 4 or more is required to be eligible for entry in to the study.

As part of the diagnostic criteria for entry in to the study, a Nugent score may be determined locally or centrally. In the event that the time taken to generate a Nugent score is unacceptable to the investigator, a local test for BV may be conducted, and the participant may be enrolled if the test is positive without confirmation of the Nugent score. If the screening Nugent score is subsequently determined to be less than 4, the participant is to be withdrawn.

At the end of the study all Gram stained slides will be independently read by two microscopists at a central laboratory for independent verification of scores. In case of discordance, a further third microscopist will assess the disputed sides. All central microscopic readers will remain blinded to treatment assignment.

If there is a discrepancy between the locally and centrally read Nugent score, the locally read score will take precedence over the centrally read score in determining whether a participant is eligible to enter the study. The centrally read score will take precedence over the local score in determining study endpoints.

7.2.6.4 Assessment of Candidiasis

The wet mount vaginal smear obtained during each pelvic exam will also be assessed for the presence of *Candida* spores. If *Candida* spores are present with symptoms of candidiasis, then oral treatment may be administered with no requirement for withdrawal post-Baseline. Once a participant has been randomized, vaginal treatments may not be administered for the period between baseline (Visit 2) and the TOC visit (Visit 4) as these may compromise the study endpoints. If oral treatment cannot be administered for the candidiasis and treatment is required prior to the TOC visit (Visit 4), then the patient must be withdrawn from the study. However, if treatment is required prior to randomization to study product, study participants will need to first be treated before randomization, and will need to comply with the inclusion/exclusion criteria (*i.e.* cannot be randomized less than 14 days after last dose of medication).

All details of candidiasis and associated treatment are to be recorded in AE and Concomitant Medication sections of the CRF. Presence of *Candida* spores alone with no symptoms of candidiasis are not to be reported as an AE.

7.2.6.5 Pregnancy Test

A urine pregnancy test will be performed at each visit, except Visit 3 (Day 9-12).

7.2.6.6 Semi-Quantitative Analysis of Vaginal Flora

A semi-quantitative culture-based assessment of various organisms will be performed at the Baseline, end of treatment (Day 9-12) and TOC Visits for a subset of 24 women. These

organisms will include: *Lactobacillus* species (H₂O₂ producing and non H₂O₂ producing), *Gardnerella vaginalis*, *Escherichia coli*, *Staphylococcus aureus*, anaerobic gram-negative rods (*Bacterioides*, *Prevotella*, *Porphyromonas*), *Enterococcus* species, Group B Streptococcus, and Candida species.

7.2.6.7 Sample for Storage

A vaginal sample is taken using a flocked swab. This is rotated in 400µl phosphate buffered saline (PBS), and frozen initially at -20°C, before final storage at -80°C. This sample will be stored indefinitely and used in the event that further analysis is required of the participants' vaginal flora.

7.2.6.8 Handling and Processing of the Biological Specimens

The handling and processing of laboratory samples is described in detail in the Study Procedures Manual.

Each study site will adhere to standards of good laboratory practice (GLP) and local SOPs for proper collection, processing, labeling, transport, and storage of specimens to the laboratories.

7.2.6.9 Storage and Destruction of the Biological Specimens

All biological samples will be destroyed once processing and reporting is complete for all study participants.

7.2.7 Symptom Questionnaire

Both Investigator-assessed and participants' perceived symptoms (*i.e.* odor and/or discharge) will be monitored throughout the study via completion of a Symptom Questionnaire, which is to be completed at Screening, Baseline (Visit 2), Day 9-12 (Visit 3) and TOC (Visit 4). The questionnaire will be split in to two sections, the first section will be a questionnaire for participants to complete, and the second section will be an assessment of symptoms by the Investigator.

Participants will be asked to indicate whether or not they have abnormal discharge and/or odor, and also to rate these two symptoms from 1 to 5 (one being normal and 5 being heavy discharge / strong odor) and compare their symptoms to the previous visit (except Screening Visit or Screen/Baseline combined visit). They will also be asked details about the discharge and odor if any is present.

Investigators will characterize the participants' discharge in terms of color, odor, and consistency. They will also provide an overall assessment of vaginal discharge as "normal" or "abnormal" based on these three characteristics, and distinguishing between normal physiological characteristics for each participant and stage of menstrual cycle (see Section 7.2.5).

7.2.8 Acceptability Questionnaire

Acceptability of the product to study participants will be determined via the use of the "Treatment Satisfaction Questionnaire for Medication, version 1.4" Acceptability Questionnaire, which has been validated in the domains of effectiveness, convenience, side-effects and overall satisfaction of medication.¹⁷ All participants will be asked to complete the Acceptability Questionnaire at the Day 9-12 Visit (Visit 3). Detailed procedures for completion of each questionnaire are outlined in the Study Procedures Manual.

7.2.9 Diary Cards

Diary cards will be employed throughout the study from Screening onwards for the study participant to record gel use (including reasons for not administering a dose), sexual activity (including details of lubricants, condoms, sex toys (sole use or shared), and type of sexual activity), signs and symptoms of genital irritation, other AEs, female menstrual history and any concomitant medication.

7.3 Study Restrictions

7.3.1 Dietary

There are no dietary restrictions during the study.

7.3.2 Confinement

Participants will only be confined at site for the duration of the study assessments outlined for each study visit. There will be no over-night confinement at the study site.

7.3.3 Physical Activity

There are no restrictions on physical activity throughout the study.

7.3.4 Sexual Activity

Although discouraged, there is no restriction on sexual activity throughout the study. All vaginal sexual activity (*i.e.* oral-vaginal, penile-vaginal or vaginal masturbation) is to be recorded in the diary card. Other details of sexual activity such as use of condoms, lubricants, sex toys (sole use or shared) or sexual activity with a new or existing partner are also to be recorded.

7.3.5 Concomitant Medication

There will be no restriction on concomitant medications administered during the study, with the exception of those outlined below:

To protect the integrity of the lower genital tract and reduce the possibility of AEs due to agents other than the study products, any spermicides, diaphragms, or contraceptive vaginal rings should not be used during this study.

Similarly, study participants requiring vaginal preparations for conditions other than their BV, such as anti-fungals, or study participants requiring antibiotics (by any route), may not be enrolled in to the study until at least 14 days after the last dose, and resolution of symptoms. Antibiotics by any route may not be administered during the on-study period, and if required will lead to cessation of study product, however participants should continue to undergo the remaining study visits. Symptoms of candidiasis occurring in study participants during the study should be treated with oral preparations where possible, if vaginally applied preparations are required, the participant will be required to withdraw from the study. All medication is to be recorded in the CRF. Participants will be required to withdraw from the study if they require treatment for an STI.

Participants will be discouraged from using additional vaginal lubricants; however, if these are used during the study, the participant will not be required to withdraw and their use is to be recorded in the concomitant medication section of the CRF.

There are no additional restrictions on concomitant medications administered during the study. However, all medications must be reported and recorded in the CRF (including prescribed and over-the-counter medications, all vitamins and herbal remedies and other traditional preparations) from the first Screening visit through to the Follow-Up visit. To avoid potential confounding of AE data (*e.g.* abrasions, changes in vaginal microflora, and allergic reactions to product components) that may be related to menstrual hygiene products (except tampons), participants will be asked to report if they have used any products and these are to be recorded in the concomitant medication section of the CRF. Use of the participant's preferred brand of tampons is acceptable and is not expected to confound AE data. Alcohol and recreational or street drug use will be recorded in the participant's study notes and CRF only if needed for interpretation/documentation of observed participant health status.

Generic or trade name should be recorded in the CRF for products with one active ingredient, or the trade name recorded for combination products, including dose, form and duration of treatment. If the concomitant medication is required as a treatment for an AE, then this must also be recorded in the CRF.

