6.9 Other Concomitant Medication/Treatment

Apart from rescue medication as outlined above, there are no concomitant medications that are to be specifically used as part of this study.

Vaginally administered products (lubricants, menstrual hygiene products (except tampons), contraception products, etc.) and oral antifungals are discouraged but should not lead to withdrawal if commenced during the study; however, the use of these is the basis for exclusion

criteria at Screening/Baseline. Antibiotics by any route are excluded during the on-study period unless provided for rescue therapy as per Section 6.8 as they will confound the study endpoints. Vaginally administered anti-fungals are also excluded during the on-study period. Women who receive antibiotic treatment (via any route) or vaginal antifungals during the study will cease study medication, but continue to be assessed during the remaining study visits. These women will not be included in the determination of the efficacy endpoints. Refer to Section 7.3.5 for more detail. Apart from concomitant medications specifically excluded under the inclusion/exclusion criteria, there are no other restrictions on concomitant treatments.

All concomitant medications administered from Screening to Follow-up must be recorded in the CRF.

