8.5 Toxicity Management

AEs and laboratory abnormalities will be graded as outlined in Section 8.3.

For the purpose of monitoring toxicities, Baseline is defined as the status or last value prior to the first use of study product. All management is based on changes from this initial status or value.

All grade 2 or higher laboratory abnormalities should be confirmed by repeat testing as soon as possible, preferably within 3 calendar days of receipt of results prior to dose interruption or discontinuation, unless such a delay is not consistent with good medical practice.

Study participants will be asked to contact the study site staff if they miss a dose of study medication due to an AE. Site staff will assess whether the participant should come in for an assessment, and if so, an ad hoc visit will be scheduled as soon as possible. In response to AEs reported by participants and/or observed upon exam by study staff, the study site investigator or designee will recommend either continuation or holding study product use consistent with the criteria in Section 16.3. Study product use also will be held or discontinued in the event of an SAE that is judged by the site Investigator or designee to have a potential causal relationship with study product.

Unless the participant withdraws consent, they will remain in the study to complete the safety evaluations (unless clinically contraindicated according to Table 1 and Section 16.3).

Participants requiring treatment for an STI will be withdrawn from the study. Participants who develop any other conditions requiring vaginal therapy (*e.g.* candidiasis) whilst on study where oral therapy cannot be used or antibiotics by any route, will cease study product, however they should continue with the remaining study visits.

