16.3.2 Follow up of findings seen on pelvic exam

| Condition / complaint | Study Gel Use | Evaluation | Follow up and Treatment Action |
|--|---|--|---|
| Localized vulval erythema involving less than 33% of introital surface with intact epithelial surfaces: | Continue at clinician's discretion | External genital visual examination | If asymptomatic, re-evaluate at next regularly scheduled visit. If symptomatic, re-evaluate in 24 hours. If worsened significantly, hold study gel use, and re-evaluate in 24 hours and reinstate study gel if resolved. Otherwise, gel may be continued or permanently discontinued at the investigator's discretion. |
| Generalized vulval erythema or severe edema; area of more than 33% of introital surface | Hold study gel use until re- evaluated | External genital visual examination | Re-evaluate in 24 hours and reinstate study gel use if resolved. |
| | | | If there is reoccurrence and there is no other etiology, then consider permanent discontinuation at the investigator's discretion. |
| Localized vaginal inflammation involving less than 33% surface area without change in usual vaginal discharge | Continue at clinician's discretion | Vaginal speculum examination | If asymptomatic, re-evaluate at next regularly scheduled visit. If symptomatic, re-evaluate in 24 hours. If worsened significantly, hold study gel use, and re-evaluate in 24 hours. If condition resolves re-instate study gel with agreement of patient at investigator's discretion. Otherwise, consider permanent discontinuation at the investigator's discretion. |
| Generalized vaginal inflammation involving >33% surface area and / or change in usual vaginal discharge | Hold study gel use until evaluated | Vaginal speculum examination | Assess vaginal microflora by PH, Gram stain and wet prep microscopy (culture for yeasts and bacterial pathogens according to local protocol). Treat according to findings as per the protocol if condition not associated with BV and re-evaluate in 24-48 hours. If treatment requires antibiotics or vaginal preparations patient must cease treatment, but is to contine study visits. May continue study gel use if symptoms improved during reevaluation. If there is recurrence, then consider permanent discontinuation. |

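### Sections 7.2.6.4 and 7.3.5 withdraw a randomized woman whose candidiasis needs vaginal treatment before TOC, while 6.9 and 8.5 have her stop gel and keep attending visits

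*Protocol*

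**What the plan says.** The case is a randomized woman who develops symptomatic candidiasis that cannot be treated orally and needs vaginal treatment before the TOC visit.

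Two sections withdraw her:
- Protocol 7.2.6.4 (Assessment of Candidiasis): "then the patient must be withdrawn from the study".
- Protocol 7.3.5 (Concomitant Medication): "if vaginally applied preparations are required, the participant will be required to withdraw from the study".

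Two sections keep her in the study without gel, and a third supports them:
- Protocol 6.9, on women who receive antibiotics "or vaginal antifungals during the study will cease study medication, but continue to be assessed during the remaining study visits".
- Protocol 8.5 (Toxicity Management), which gives candidiasis as its example of a condition needing vaginal therapy, "where oral therapy cannot be used or antibiotics by any route, will cease study product, however they should continue with the remaining study visits".
- Protocol 16.3.2, in the row on generalized vaginal inflammation: "If treatment requires antibiotics or vaginal preparations patient must cease treatment, but is to contine study visits". This covers vaginal preparations in general and is not a candidiasis rule.

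Section 6.9 then sends the reader on: "Refer to Section 7.3.5 for more detail". It also says of these women: "These women will not be included in the determination of the efficacy endpoints".

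**The concern.** A site cannot follow both instructions, and its choice changes what is recorded. Section 8.2.1 runs AE reporting from first dose to TOC, and 10.2.6.4 keeps every randomized and dosed woman in the Safety dataset. If one site withdraws such women and another keeps them, women in the same safety tables have been observed for different lengths of time. The affected women all had candidiasis, whose incidence is a planned output in 10.10. The same clinical event would also appear in the disposition data as a withdrawal at one site and not at another.

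**Working it through.** The plan gives no figure on this point, so there is none to reproduce. The check is a comparison of sections, followed by simple day counts.

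**1. Is the scope the same?** Yes. Sections 7.2.6.4 and 8.5 both address candidiasis after randomization where oral therapy is not possible. Section 6.9 covers receipt of vaginal antifungals during the study, which is the same treatment.

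**2. Could the two outcomes be loose synonyms?** No. Section 7.3.5 uses both. For a woman who needs antibiotics, the need "will lead to cessation of study product, however participants should continue to undergo the remaining study visits", whereas a woman who needs vaginal treatment for candidiasis is withdrawn. Section 8.5 also separates them: treatment for an STI means withdrawal, and candidiasis needing vaginal therapy means stopping product and continuing.

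**3. Does anything settle it?** Not explicitly. The cross-reference in 6.9 leads to the section that says the opposite. Section 9.3 lists interfering medication among acceptable reasons for withdrawal but is permissive, so it does not choose between two mandatory rules. The nearest to a tie-breaker is the general default in 8.5 that participants who have not withdrawn consent stay in to complete the safety evaluations unless this is clinically contraindicated.

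**4. How much routine AE collection is lost per affected woman?** Gap = TOC day minus Withdrawal Visit day, with TOC on Day 21-30 (Table 1).

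| Withdrawal Visit | Shortest gap | Longest gap |
|---|---|---|
| Day 2-8 (need arises around dosing) | 21 - 8 = 13 days | 30 - 2 = 28 days |
| Day 9-12 (at Visit 3) | 21 - 12 = 9 days | 30 - 9 = 21 days |
| Day 21 | 21 - 21 = 0 days | 30 - 21 = 9 days |

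The visit days are examples. Section 7.1.6 asks for the Withdrawal Visit promptly, with two weeks after the end of treatment as a target and not a limit.

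**5. What does the withdrawal coding affect?** Section 9.5 allows replacement, at the sponsor's discretion, once on-study withdrawal exceeds 15% and half of planned recruitment (132/2 = 66) is reached. The rate may be taken at any point after that:
- 66 women: 9/66 = 13.6%, 10/66 = 15.2%
- 79 women: 11/79 = 13.9%, 12/79 = 15.2%
- 132 women: 19/132 = 14.4%, 20/132 = 15.2%

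One woman's coding matters only when the count is next to the threshold. Section 10.2.6.1 defines completion as at least 6 doses and attendance at all visits, so a woman treated after her sixth dose could be a completer under one rule and a withdrawal under the other.

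**6. Do the efficacy sets change?** There are two branches.
- *She receives the vaginal antifungal while on study.* Sections 6.9 and 10.2.6.3 take her out of the MITT set under either rule. The per-protocol set is a subset of MITT, so it does not change either.
- *She is withdrawn because the treatment is needed, and is treated only afterwards.* The withdrawal rules act on need, and 7.2.6.4 bars vaginal treatment between Baseline and TOC. The MITT exclusion acts on receipt. If she has taken a dose and has a post-baseline efficacy assessment, possibly from the Withdrawal Visit itself, 10.2.6.3 does not clearly exclude her, and 10.8 would fill her missing TOC value by LOCF.

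**The case against.** The strongest reply is that little is lost. The Withdrawal Visit repeats the TOC procedures (Table 1, footnote 2), so the Amsel assessment, Gram stain, questionnaire and pregnancy test are brought forward and not dropped. Section 8.3 has AEs present at withdrawal followed until resolved or stable, and 8.2.2 runs SAE reporting to 30 days after the last dose. Attendance at TOC is not universal anyway, since 9.2 excuses non-responders at Visit 3. The 8.5 default already points sites toward keeping her in. All of this stands. It limits the loss to new non-serious AEs arising after the Withdrawal Visit, but it does not cancel two sections that make withdrawal mandatory.

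It may also be said that aligning the text in either direction would remove the contradiction. That is true; the choice of direction rests on the 8.5 default and on keeping safety follow-up.

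Two stronger readings are tempting. A reader might infer that the primary efficacy result is at risk. The documents do not support this: the usual branch leaves both efficacy sets unchanged, and the other leaves membership unclear for an unknown number of women. The opposite inference, that efficacy cannot be touched at all, also goes too far because of that second branch. A reader might also infer a bias between arms in the safety comparison. Sites are blinded, and nothing in the protocol ties a site's reading of the rule to treatment arm.

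**Conclusion.** The contradiction is real and concerns one well-defined case. Its consequence is minor. For a woman with at least one dose, the withdrawal rule shortens routine detection of new non-serious AEs, by 9 to 21 days in the Visit 3 example, and codes her as a withdrawal. For a woman randomized but never dosed, the safety consequence does not arise, because she is outside the Safety dataset. The protocol does not say how many women will be affected, and none is assumed; the number could be zero. The efficacy sets are unchanged if treatment is received on study, and MITT status is unclear only if withdrawal comes before treatment.

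**What to change.** Amend one sentence in 7.2.6.4 and one in 7.3.5: a randomized woman who needs vaginal treatment for candidiasis before TOC stops study product but attends all remaining visits, including TOC, with AE collection throughout. This matches 6.9, 8.5 and 16.3.2.

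Keep the MITT exclusion for vaginal antifungal use as written. Because she would then be treated while on study, the exclusion applies to her without doubt and the unclear branch closes. Section 9.3 may stay: it still lets an investigator withdraw a woman on judgment, so some variation between sites can remain, but it no longer conflicts with a mandatory rule.

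The cost is two sentences in a protocol amendment. The visits are already scheduled, and the sample size, dataset definitions and planned analyses stay as they are.
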